4.7.2. Clinical Laboratory Tests

Blood and urine samples will be collected for clinical laboratory evaluations (including clinical chemistry, hematology, urinalysis, and serology) at the time points specified in Protocol

Appendix 1. The data collected in different units were converted to SI units (the International System of Units) for summary.

The following summaries by study periods will be provided by laboratory category of chemistry, hematology, and urinalysis.

- Numeric laboratory values will be summarized as descriptive statistics for both actual value and change from baseline (post baseline minus baseline) by week. If lab values are recorded as <xx, the limits of xx will be used for summary.
- Shift table summarizing subject incidence of laboratory normal range (Low, Normal, High) at baseline contrasted with lowest or highest post baseline. Parameters with bidirectional abnormality (low and high) will be presented by post baseline lowest and highest.

All laboratory data will be listed.

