8. Presence of severe depression as indicated by PHQ-9 total score of  $\geq 20$  or item 9 score  $> 0$  at the Screening Visit or Day 1.
9. Presence of severe anxiety as indicated by GAD-7 score of  $\geq 15$  at the Screening Visit or Day 1.
10. Presence of severe chronic pain (e.g., back pain, migraine, osteoarthritis, etc., defined as  $\geq 7.0$  on 0 to 10 NRS scale with 0 being no pain and 10 being the worst pain possible) at the Screening Visit.
11. Presence of uncontrolled hyperthyroidism or hypothyroidism or uncontrolled diabetes defined as hemoglobin A1c  $> 7.5\%$ .
12. Presence or history of cancer or lymphoproliferative disease within 5 years prior to Screening Visit, with the exception of basal and squamous cell carcinoma of the skin or in situ carcinoma of the cervix successfully treated and considered controlled.
13. Presence or history of immune deficiency, or opportunistic infections.
14. Positive results for hepatitis B surface antigen (HbsAg) and/or hepatitis B anti-core antibody (anti-HBc) but negative results for anti-surface antibody (anti-HBs) at the Screening Visit.
15. Positive results for hepatitis C antibody unless patient received curative therapy and a negative viral load is documented.
16. Human immunodeficiency virus (HIV) infection or positive HIV serology at the Screening Visit.
17. Positive COVID-19 viral test at Screening Visit or suspected COVID-19 infection at Baseline Visit.
18. Subject is on hemodialysis or peritoneal dialysis.
19. Latent or active TB, as determined by a positive Quantiferon-based TB test result at Screening Visit.
20. Laboratory abnormalities that fall outside the windows below at the Screening Visit:
  - a. Alanine aminotransferase  $> 3 \times$  upper limit of normal (ULN)
  - b. Aspartate aminotransferase  $> 3 \times$  ULN
  - c. Gamma-glutamyl transferase  $> 3 \times$  ULN
  - d. Blood bilirubin  $> 2 \times$  ULN
  - e. Hemoglobin more than 1g/dL below the lower limit of normal for sex per the laboratory in which screening lab is performed
  - f. Platelet count  $< 150,000/\mu\text{L}$

g. Neutrophil count <1,500/ $\mu$ L

21. Major surgery within 12 weeks prior to Day 1 or has a major surgery planned during the study.
22. Has an active infection, including skin infection, requiring systemic treatment within 4 weeks and/or topical treatment within 2 weeks of Day 1. Subject has an active or chronic parasitic infection.

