#### **8.7.2 Clinical and Laboratory Events and Analyses**

Continuous laboratory data will be examined for trends using descriptive statistics of actual values and changes from baseline over time in each treatment group. These data will also be categorized as low, normal, or high based on the reference ranges of the central laboratory. Shift tables from baseline to each post baseline time point will be presented.

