3. GENERAL CONSIDERATIONS

All analyses and summaries will be produced using SAS® version 9.4 (or higher).

For inferential statistical analyses, each arm of KPL-716 (Arm A KPL-716: 540 mg Q4W, Arm B KPL-716: 360 mg Q4W, Arm C KPL-716: 120 mg Q4W) will be compared to placebo. Unless otherwise specified, all tests will be at two-tailed using pre-specified level of significance 0.05.

Descriptive statistics (n, mean, standard deviation [SD], median, Q1, Q3, minimum, and maximum) will be presented for continuous variables. For continuous efficacy endpoints, least square (LS) mean, LS mean difference, standard error (SE), and 95% confidence interval (CI) will be calculated.

For categorical variables (including binary variables), counts and percentages will be presented. For binary efficacy endpoints, 95% CI for difference in proportion and p-values will be presented.

Subject listings in all randomized subjects, will be provided for all efficacy and safety data. In general, the subject listings will be sorted by treatment group, subject number and assessment date (and time, if applicable).

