4.2.2. Baseline and Disease Characteristics

The following baseline characteristics will be summarized.

- Years since first PN nodules (calculated relative to first dose date)
- Years since diagnosis (calculated relative to first dose date)
- Elevated IgE: High ($>200 \text{ IU/mL}$), normal ($\leq 200 \text{ IU/mL}$)
- Co-morbidities includes, but not limited to, history of atopy, anxiety or depression, allergy, dermatologic conditions, lipid disorders, hypertension, type 2 diabetes, and chronic renal disease.
- Smoking status
- Treated with KPL-716 in previous KPL-716 studies (yes, no)

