4.7.4. Electrocardiograms

Numeric 12-lead ECG parameters will be summarized. Descriptive statistics will be presented for the observed value and the change from baseline at each scheduled visit. Incidence of a normal to abnormal shift for overall ECG interpretation from baseline to worst post baseline will also be summarized by periods. Findings of other categorical parameters will be listed. For repeated assessment, if interpretations are the same, the last value will be taken for numerical assessment for summaries. If interpretations are different, the last value with the abnormal interpretation will be used for summary.

QT interval corrected for heart rate using Fridericia's method - Below incidence will be summarized:

- QTcF interval >500 msec
- QTcF change from the baseline (pre-dose) is >60 msec

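### SAP 4.7.2 counts no subjects by size of laboratory abnormality, and its Low/Normal/High shift table cannot show enzymes already High at baseline rising further

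*SAP*

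**What the plan says.** SAP 4.7.2 plans three laboratory outputs.

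- By-week summaries: "Numeric laboratory values will be summarized as descriptive statistics for both actual value and change from baseline (post baseline minus baseline) by week". SAP Section 3 defines the content: "Descriptive statistics (n, mean, standard deviation [SD], median, Q1, Q3, minimum, and maximum) will be presented for continuous variables".
- A shift table: "Shift table summarizing subject incidence of laboratory normal range (Low, Normal, High) at baseline contrasted with lowest or highest post baseline". Tests that can be abnormal in both directions are shown for both the lowest and the highest value.
- Listings: "All laboratory data will be listed".

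Protocol 8.7.2 uses the same three classes: "These data will also be categorized as low, normal, or high based on the reference ranges of the central laboratory". Neither document plans an incidence by multiple of ULN, by toxicity grade or by multiple of baseline, or a combined transaminase and bilirubin count.

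Exclusion criterion 20 (Protocol 4.7.2) covers "Laboratory abnormalities that fall outside the windows below at the Screening Visit". It excludes ALT, AST and GGT only above 3×ULN, bilirubin only above 2×ULN, and hemoglobin only when more than 1 g/dL under the lower limit. It sets no creatinine limit. The co-morbidities to be tabulated in SAP 4.2.2 include "type 2 diabetes, and chronic renal disease".

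For by-visit safety summaries, SAP 3.3 takes the measurement nearest the target day when a window holds several. Protocol 7.5.3 has clinically significant abnormal results after Screening reported as adverse events. For ECGs, SAP 4.7.4 does count threshold crossings: QTcF above 500 msec, and "QTcF change from the baseline (pre-dose) is >60 msec".

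**The concern.** A three-class shift table answers one question: did a result leave the normal range? It does not say how far. Two consequences follow.

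- An enzyme that is High at baseline has no worse class to move to, and the entry limits allow such baselines.
- A trivial and a large rise from normal fall in the same cell.

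Without a table that counts subjects by size of abnormality, the arms cannot be compared on the number with a large liver, renal or blood-count change.

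This matters because the study is meant to inform dose and regimen for later trials of a first-in-class antibody (Protocol 1.3), and Protocol 1.5 accepts that unknown adverse events may appear with longer exposure. The Safety Review Team is blinded (Protocol 7.5.7) and no DMC meets (SAP Section 5). The final tables are therefore where laboratory safety will be compared by dose.

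**Working it through.** The plan states no figure on this point, so the check is mainly logical. The only plan figure used is the arm size. SAP 1.5 needs 38 per arm and allows 15% dropout: 38/(1 − 0.15) = 44.7, rounded up to 45, and 4 × 45 = 180. Both agree with the SAP.

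**1. Apply the planned classes to an enzyme.** High means above 1×ULN. The 3× cut-off is the entry limit; 5× is assumed for illustration.

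| Baseline → worst value (×ULN) | Planned cell | >3×ULN | >5×ULN |
|---|---|---|---|
| 0.8 → 1.1 | Normal→High | no | no |
| 0.8 → 10 | Normal→High | yes | yes |
| 1.1 → 1.1 | High→High | no | no |
| 1.1 → 10 | High→High | yes | yes |
| 3 → 3 | High→High | no | no |
| 3 → 10 | High→High | yes | yes |

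Six different courses fill two cells. Hemoglobin is the mirror image: a subject admitted slightly below the lower limit starts Low, and a further fall stays Low.

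**2. Incidence by arm (hypothetical).** Suppose 6 of 45 subjects shift Normal to High in each of two arms. In one arm all stay at or below 1.5×ULN; in the other, three exceed 5×ULN. The shift table shows 6/45 = 13.3% in both.

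The by-week maximum would separate these two arms if the peaks fell on the values selected for the visits. It would not separate one subject above 5×ULN at three visits (1/45 = 2.2%) from three subjects above 5×ULN at one visit each (3/45 = 6.7%), since both can give the same run of maxima.

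**3. Means.** If three of 45 subjects rise by 5×ULN (from 1× to 6×), each at one of the five post-baseline double-blind visits, the average visit mean moves by (3/5) × 5/45 = 0.07×ULN. One subject going from 1.1× to 10×ULN moves it by (10 − 1.1)/45 = 0.20×ULN, or 8.9/38 = 0.23×ULN with 38 subjects.

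**4. Would cases occur at all?** The documents give no rate, so the following are assumptions. The chance of at least one case among 45 is 1 − (1 − p)^45: 36% at p = 1%, 60% at 2% and 90% at 5%. These are chances that a case occurs, not that it is missed.

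**5. Off-schedule peaks.** The by-visit rule keeps one value per window. The Week 32 OLE window for blood tests runs from Day 72 to Day 169 after the first OLE dose (169 − 72 + 1 = 98 days). A repeat sample far from the target day can be dropped from the by-week maximum. The SAP does not say whether unscheduled values enter the lowest or highest value in the shift table.

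**The case against.** A reader might infer that laboratory data are summarised only as means, that no table by arm can show how large an abnormality was, or that a subject High at baseline can never be seen to worsen. The documents do not support any of these.

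- The SAP's descriptive statistics include minimum and maximum, for both value and change, by treatment, visit and period (SAP 3, 4.7 and 4.7.2). A rise from 3× to 10×ULN at a scheduled visit would appear as a change of 7×ULN or be exceeded by a larger one.
- Every value is listed.
- Clinically significant findings, including worsening of a pre-existing condition, go to the adverse event tables by arm and severity (Protocol 7.5.1.1, 7.5.3 and 8.7.1).
- The ceiling and the identical cells are features of the shift table alone. A bidirectional test can still move from High to Low.

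It can also be said that no document states how many subjects start with raised enzymes. Listing co-morbidities gives no frequency, and entry excludes certain hepatitis results, uncontrolled diabetes, dialysis and alcohol abuse. No hepatic, renal or blood-count concern is described, and the only named event of special interest is angioedema. The QTcF thresholds repeat the protocol's own triggers for repeat ECGs (Protocol 7.5.5), so their presence does not make the laboratory plan inconsistent.

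All of this stands, and it limits the size of the point. It does not remove it. The maximum is one number per arm and visit, is not planned in multiples of ULN, counts nobody and can miss an off-schedule peak. The adverse event route depends on the investigator judging a result clinically significant. Listings give no incidence by arm.

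**Conclusion.** The point holds in this form: no planned output counts subjects, by arm, by size of laboratory abnormality, and the Low/Normal/High shift table cannot show further worsening of enzymes already High at baseline or separate 1.1× from 10×ULN in subjects who start Normal. The other outputs partly compensate.

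The size cannot be fixed from the documents, because neither the share of subjects with raised baselines nor any rate of large abnormalities is given. The 13.3%, 2.2% and 6.7% figures are hypothetical counts in arms of 45, and the 36% to 90% range rests on assumed rates of 1% to 5%. None of them measures a loss of safety information.

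This is a low-cost improvement to safety reporting. It does not affect the efficacy analyses, and it does not imply that a signal is expected.

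**What to change.** Keep the planned summaries, shift table and listings. Add to SAP 4.7.2, by arm and study period, a table of baseline against worst post-baseline value that uses all post-baseline values, including unscheduled ones. For key tests:

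- ALT, AST, GGT and bilirubin in multiples of ULN, with the protocol's entry limits (3×ULN for the enzymes, 2×ULN for bilirubin) among the cut-points, plus higher multiples such as 5× and 10×ULN for the enzymes.
- The number of subjects with ALT or AST above 3×ULN together with bilirubin above 2×ULN.
- Creatinine as a multiple of baseline.
- Graded decreases in platelets, neutrophils and hemoglobin, with the grading scale named in the SAP.
- For subjects above ULN at baseline, multiples of baseline as well.

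The higher multiples and the grading scale have no source in the documents and are the sponsor's to choose before unblinding. All cut-points are for reporting only and set no clinical management rule.

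The cost is a SAP wording change and one or two extra tables from data already collected, with no new samples or visits. While the section is open, one related difference should be reconciled: Protocol 8.7.2 plans shifts to each post-baseline time point, SAP 4.7.2 uses the lowest or highest value, and SAP Section 6 declares no changes.

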4.7.3. Vital Signs

All vital signs including weight, pulse rate, body temperature, respiration rate, and systolic and diastolic blood pressure will be summarized. Descriptive statistics will be presented for the observed value and the change from baseline by treatment and visit if applicable. For repeated assessments at a visit, the average of these values will be taken for the summary at the visit.

4.7.4. Electrocardiograms

Numeric 12-lead ECG parameters will be summarized. Descriptive statistics will be presented for the observed value and the change from baseline at each scheduled visit. Incidence of a normal to abnormal shift for overall ECG interpretation from baseline to worst post baseline will also be summarized by periods. Findings of other categorical parameters will be listed. For repeated assessment, if interpretations are the same, the last value will be taken for numerical assessment for summaries. If interpretations are different, the last value with the abnormal interpretation will be used for summary.

QT interval corrected for heart rate using Fridericia's method - Below incidence will be summarized:

- QTcF interval >500 msec
- QTcF change from the baseline (pre-dose) is >60 msec

4.7.5. Physical Examination

Clinically significant new or worsened physical examination abnormalities following treatment will be recorded as AEs and will be reflected in the summary of AEs.

4.7.6. COVID-19 infection

If there are new COVID-19 infections during the trial, their incidence and severity will be analyzed per treatment group to explore any potential dose-relationship of COVID-19 susceptibility, and the impact of COVID-19 infection on efficacy and safety as well. Gender difference on COVID-19 infection may be explored if a significant number of events are observed.

If a COVID-19 outbreak occurs at a particular investigational site, a sensitivity analysis may be conducted to evaluate the impact on trial results.

4.8. Immunogenicity Analysis

Pre-dose anti-drug antibody (ADA) blood samples will be collected according to schedule in protocol appendix 1.

ADA status will be categorized as follows.

1. Treatment-emergent ADA, including treatment induced or boosted [increased by one quartile (with all titers collected) from baseline]
2. Prior existing ADA (without treatment boosted)
3. ADA negative at every assessment.

For subjects with treatment-emergent ADA, the maximum post-baseline titer level (low, medium, high) will be summarized. The 3 levels (low, medium, high) will be divided based on 25th and 75th percentiles from all ADA titers pooled.

Subjects with Neutralizing antibody will be summarized for subjects with treatment-emergent ADA and non-treatment-emergent prior existing ADA.

A summary table will be provided for number and percent of subjects with positive or negative anti-KPL-716 antibody by visit. An individual's ADA status and titer level (if positive) at each visit will be provided. The number and percent of subjects with anti-KPL-716-antibody positive at any visit vs. those with negative at every visit will also be provided.

Details are in a separate analysis plan and analysis results are also reported in a separate report.

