#### **8.10 Immunogenicity Analyses**

Serum ADA will be listed and summarized by treatment group and overall using descriptive statistics.

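### SAP 4.8 defines boosted ADA by a step up in quartile, so on the ordinary reading a baseline titer already in the top quartile cannot be classed as boosted

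*SAP*

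**What the plan says.** SAP 4.8 sorts subjects into three ADA groups. The first is treatment-emergent ADA, either induced by treatment or boosted by it, where boosted means "increased by one quartile (with all titers collected) from baseline". The second is "Prior existing ADA (without treatment boosted"). The third is ADA-negative throughout. The section gives no fold-rise or dilution-step criterion, no rule for titers that fall on a cut, and no exception for baselines already in the highest quartile.

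The group decides later summaries. "For subjects with treatment-emergent ADA, the maximum post-baseline titer level (low, medium, high) will be summarized", so only the first group enters that table. The neutralizing-antibody summary is also split by treatment-emergent status. For the titer levels the SAP states: "The 3 levels (low, medium, high) will be divided based on 25th and 75th percentiles from all ADA titers pooled".

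The section closes: "Details are in a separate analysis plan and analysis results are also reported in a separate report". Protocol 8.10 does not define boosting and promises only description: "Serum ADA will be listed and summarized by treatment group and overall using descriptive statistics". Both documents list immunogenicity as an exploratory objective (Protocol 2.3, SAP 1.1.3).

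**The concern.** Boosting is a change within a subject. The SAP measures it on a scale set by everyone's titers, and that scale has a ceiling. Three consequences follow on the ordinary reading.

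- **Ceiling.** A baseline in the fourth quartile has nowhere to go, so the subjects with the highest existing titers cannot be recognised as boosted.
- **Uneven sensitivity.** The rise needed depends on where the baseline lies relative to the cuts. A several-dilution rise may not count, while a one-dilution rise elsewhere does.
- **Dependence on others.** The cuts use all collected titers, including any raised by the drug. A subject's status can change although that subject's own titers have not.

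At stake is the split between treatment-emergent and prior existing ADA among subjects who enter with antibodies. The plan expects such subjects. It has a category for them, SAP 4.2.2 tabulates previous treatment with KPL-716, and exclusion criterion 2 bars drugs against this receptor only within the past 3 months.

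**Working it through.** The documents give no titers, so there is no figure of the plan's to reproduce. The check applies the rule as worded to assumed titers. All titer values below are assumptions.

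**1. Rule applied.** Take the 25th, 50th and 75th percentiles of all titers, assign each titer to quartile 1 to 4, and call a subject boosted if the post-baseline quartile exceeds the baseline quartile. A titer equal to a cut goes to the lower quartile unless stated.

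**2. Ceiling and uneven sensitivity.** Assumed pool of 12: 10, 20, 20, 40, 40, 80, 80, 160, 160, 320, 640, 1280. The interpolated cuts are:
- 25th: 20 + 0.75 × (40 − 20) = 35
- 50th: 80
- 75th: 160 + 0.25 × (320 − 160) = 200

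| Baseline | Quartile | 2-fold rise | 4-fold rise | 16-fold rise | 64-fold rise |
|---|---|---|---|---|---|
| 20 | 1 | boosted | boosted | boosted | boosted |
| 40 | 2 | not | boosted | boosted | boosted |
| 160 | 3 | boosted | boosted | boosted | boosted |
| 320 | 4 | not | not | not | not |

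A 64-fold rise from 320 is not boosted; a 2-fold rise from 20 is. The zero for top-quartile baselines follows from the definition and is not an estimate.

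**3. Ties.** In the same pool 80 is the median cut. With ties to the lower quartile, 40 to 80 is not boosted and 80 to 160 is. With ties to the upper quartile, both answers reverse.

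**4. Dependence on the pool.** Add four later titers of 640 from other subjects. Of the 16 ordered values, the 4th and 5th are 40, the 8th and 9th are 160, and the 12th and 13th are 640, so the cuts become 40, 160 and 640. A subject going from 320 to 1280 was in quartile 4 both times and not boosted; the same subject now goes from quartile 3 to 4 and is boosted. In this pool a 4-fold rise from 10 to 40 stays in quartile 1 and is missed, while a 2-fold rise from 160 to 320 counts. This could matter in practice. The Schedule of Activities collects ADA to Week 52, and SAP 3.5 allows an analysis after the double-blind period and a final one with open-label data. If ADA is summarised at both, the cuts can move between them.

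**5. Can a miss rate be given?** A simulation used 200,000 baselines, log2 titers normal and rounded to whole dilutions, SD 1.5, 2 or 3, and quartiles from an independent pool with the same distribution:

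| True rise | Flagged as boosted (SD 1.5 / 2 / 3) | Missed |
|---|---|---|
| 2-fold | 0.683 / 0.548 / 0.345 | – |
| 4-fold | 0.793 / 0.668 / 0.676 | 21 to 33% |
| 16-fold | 0.839 / 0.762 / 0.765 | 16 to 24% |

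Two unspecified choices move these figures:
- **Tie rule.** Sending ties to the upper quartile raises the misses to 37–44% for 4-fold rises and 32–40% for 16-fold rises.
- **Make-up of the pool.** With five drug-raised titers per baseline in the pool, the share of baselines in the top quartile falls from 16–23% to 1–7% for 4-fold rises and to 0–1.5% for 16-fold rises. Most misses then occur inside lower quartiles. With 20 baseline-positive subjects and 60 induced titers (log2 SD 2), the top-quartile share ran from about 2% to 28%.

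The direction of the fault is clear. Its size cannot be obtained from the documents.

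**The case against.** The strongest reply is that SAP 4.8 is only a summary. It defers details to a separate plan, which may hold a fold-rise criterion or a top-quartile rule. That cannot be checked here and stands as a limit on the point. Even so, the SAP states a rule that can be applied as written, and the two documents should agree.

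The wording is also loose. If one quartile meant a fixed amount, such as the interquartile width, the ceiling would vanish: in the 12-titer pool the width is 200 − 35 = 165, and a rise from 320 to 1280 is 960. The SAP defines no such amount, and the word pooled appears only in the sentence on titer levels. The ceiling therefore rests on the ordinary reading, and the need to guess is itself a reason to clarify.

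Other outputs limit the harm. Section 4.8 also provides positive and negative counts by visit, any-visit positivity, each subject's status and titer level by visit, and neutralizing antibody in the prior existing group. A missed subject loses a label and a place in one table but is still reported.

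A reader might infer that the trial's treatment-emergent ADA rate is unreliable as a whole, or that the rule misses a known share of boosts, such as a fifth to a third of 4-fold rises. The documents support neither. Treatment-induced ADA does not use the quartile rule, no titers or baseline prevalence are given, and the simulated percentages change with the tie rule and the pool.

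**Conclusion.** The point holds as a minor defect of definition. On the ordinary reading, SAP 4.8 cannot class a top-quartile baseline as boosted. It detects equal fold-rises unequally and ties each subject's status to other subjects' data. Misclassified subjects move to the prior existing group and leave the maximum post-baseline titer summary.

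The effect reaches only subjects who are ADA-positive at baseline and whose titer then rises. Their number is not given and may be small. It does not reach treatment-induced ADA or any efficacy result, and SAP 4.8 attaches no test or decision to ADA status. The conclusion assumes that one quartile means a step up among quartiles of all collected titers, and that the separate immunogenicity plan does not already say otherwise.

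**What to change.** In SAP 4.8, aligned with the separate immunogenicity plan, define boosted as a post-baseline titer at or above a fixed multiple of the subject's own baseline titer. Set the multiple before unblinding and above one dilution step of the assay; two steps would be one choice, but the dilution scheme is not in the documents and must come from the assay. Keep the pooled 25th and 75th percentiles only for the low/medium/high display, and state there which level a titer equal to a cut joins. If the separate plan already holds such a rule, cite it in SAP 4.8 and remove the quartile wording.

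The cost is one definition in two documents and the matching programming. It needs no new samples or visits and does not affect the sample size.
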